8.5 Prior and Concomitant Medication

The SCD subjects will be allowed to take the medications as needed with the exception of those described listed in Section 7.2.3. All concomitant medication will be documented.

In the interests of subject safety and acceptable standards of medical care the Investigator will be permitted to prescribe treatment(s) at his/her discretion. All treatments must be recorded in the subjects' case report form (CRF) (medication, dose, treatment duration and indication).

Subjects will be provided with a diary card for completion during outpatient periods and will be instructed to document in the diary all details of AEs, and details of any medication taken

8.6 Method of Assigning Subjects to Treatment Groups

Following confirmation of continued eligibility subjects will be assigned to the following treatment groups:

Group 1

Subjects from Cohort 17 in the GBT440-001 study who have received GBT440 900 mg per day for 4 months will continue receiving GBT440 900 mg per day for a further 2 months in this study.

Group 2

Subjects from Cohort 17 in the GBT440-001 study who have received placebo for 4 months will receive GBT440 900 mg per day for 6 months in this study.

Group 3

Subjects from Cohort 15 in the GBT440-001 study who have received GBT440 600 mg per day for 2 months will continue receiving GBT440 600 mg for a further 4 months in this study or the dose may be increased if the subject has tolerated 600 mg in GBT440-001.

Group 4

Subjects from Cohort 15 in the GBT440-001 study who have received placebo for 2 months will receive GBT440 900mg per day for 6 months in this study.

Group 5

Subjects from Cohort 7, 11, 12, 14, 16 or 17 who received either GBT440 or placebo who are enrolled into this study will receive GBT440 at a dose of 900 mg per day for a total of 6 months in this study.

All Subjects will receive a total of 6 months treatment with GBT440 which will include treatment with GBT440 in the GBT440-001 study for subjects in Cohort 15 or 17.

Subjects from Cohort 7, 11, 12, 14, 16 or 17 who received either GBT440 or placebo will receive a total of 6 months of treatment with GBT440 in this study.

8.7 Randomisation Procedures

Not Applicable – this is an open label single arm study in which all subjects will receive GBT440.

9.0 STUDY PROCEDURES

Table 2 Estimated Blood Volumes:

Assessment	Sample Volume (mL)	No. of Samples	Total Volume (mL)
Sickle Cell Disease Subjects: Multiple Dose			
Safety			
Serum Biochemistry	3.5	Up to 10	35.0
Coagulation	1.8	Up to 8	14.4
Haematology	2.0	Up to 10	20.0
Pregnancy	3.5	8	28.0
Hba1c	3.5	7	24.5
Pharmacokinetic			
GBT440	2.0	11	22.0
Pharmacodynamic			
Serum erythropoietin (EPO)	3.5	Up to 8	28.0

Assessment		Sample Volume (mL)	No. of Samples	Total Volume (mL)
	Frozen Plasma Reserved for immunology/inflammation and exploratory markers	5.0	Up to 8	40.0
	Haemoglobin electrophoresis	2.0	Up to 4	8.0
	Carboxyhaemoglobin	2.0	Up to 7	14.0
Disease Related				
	Dense Cells	2.0	Up to 8	16.0
	NT pro-BNP	2.0	Up to 8	16.0
Total [b]				335.9

Sample volumes are based on direct venipuncture.

9.1 Pharmacokinetic Assessments

Serial whole blood samples will be obtained from all and SCD subjects at the times shown in the schedule of events (see Section 17.0) for the determination of GBT440 concentrations in whole blood and plasma.

Blood and plasma samples will be analyzed for GBT440 using a validated liquid chromatography-tandem mass spectrometry (LC-MS/MS) method.

9.2 Pharmacodynamic/Treatment Response Assessments

Sample collection and assessment times are included in the schedule of events (see Section 17.0).

9.2.1 Haemolysis markers:

Haemoglobin, unconjugated bilirubin, LDH, absolute and % reticulocyte counts and % dense cells will be measured.

9.2.2 Disease Related Assessments:

Inflammatory markers and exploratory biomarkers related to SCD disease severity will be assessed and may include, but are not limited to:

- Serum erythropoietin
- Urine microalbumin
- Plasma cytokines or other exploratory markers of SCD
- Haemoglobin F levels
- Immune and Inflammatory plasma biomarkers (e.g. inflammatory cytokines)

9.3 Safety Assessments

9.3.1 Adverse Events

Any untoward medical occurrence in a patient or clinical investigation subject administered a pharmaceutical product and which does not necessarily have to have a causal relationship with this treatment.

An AE can therefore be any clinically significant sign (including an abnormal laboratory finding, for example), symptom, or disease temporally associated with the use of a medicinal product, whether or not considered related to the medicinal product.

Adverse Drug Reaction (ADR)

Any untoward and unintended response in a subject to an IMP which is related to any dose administered to that subject.

Serious Adverse Event (SAE)

An adverse reaction is ‘serious’ if it:

- Results in death;
- Is life-threatening;
- Requires hospitalization or prolongation of existing hospitalization;
- Results in persistent or significant disability or incapacity;
- Consists of a congenital anomaly or birth defect;
- Is a medically important event.

Unexpected Adverse Reactions

An adverse reaction is ‘unexpected’ if its nature and severity are not consistent with the information about the medicinal product in question set out:

- In the case of a product with a marketing authorization, in the summary of product characteristics for that product;
- In the case of any other IMP, in the Investigator’s Brochure relating to the trial in question (Investigator’s Brochure Version 3, 2016).

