7.1.1 Stopping Rules

Individual subject stopping rule

- Dosing for any individual subject will be stopped if the subject experiences a serious adverse event (SAE) or a clinically significant non serious AE, which in

the opinion of the Principal Investigator or Sponsor's Medical Monitor, warrants discontinuation of the study for that subject's wellbeing.

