8.3 Dose Modification

Dose modification may be considered if warranted and as outlined below. All instances of study drug modification (change in dosing frequency, dose reduction or discontinuation) are to be captured in the subject research record and on the CRF and will require prompt notification of the medical monitor (i.e., typically within 48 hours). If the conditions/event leading to the dose modification have resolved, the original dose level and once a day dosing frequency should be resumed, unless in the judgement of the investigator, this cannot be done safely. Dose reductions will be made in 300 mg increments.

Dose level may be reduced for:

- Mild or moderate (Grade ≤ 2) adverse events that persist for ≥ 72 hours.
- Moderate (Grade ≥ 2) adverse events that require intervention (excluding over the counter symptomatic treatment such as acetaminophen, NSAIDs, antacids, antihistamines), that in the Investigator's judgement are deemed study drug related.
- Severe (Grade ≥ 3) adverse events that are not serious and that in the Investigator's judgement are deemed study drug related.

Study drug may be suspended for:

- Any AE that, in the opinion of the Investigator is drug related and warrants suspension of dosing.

- Re-initiation of dosing will be based on the Investigator's clinical assessment in consultation with the sponsor.
- If the conditions/event leading to the dose suspension have improved or resolved, dosing should be resumed at the original dose level and once a day dosing frequency, unless in the judgement of the investigator, this cannot be done safely.

Study drug may be discontinued for:

- Grade ≥ 3 drug-related SAE
- Any AE that, at the discretion of the Investigator, warrants discontinuation of study drug.

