9.3.2 Reporting of Adverse Events

All AEs must be fully recorded in the AE book throughout the entire study period and will be transcribed into the subjects’ CRF, whether or not they are considered to be drug-related. Signs and symptoms of each AE should be described in detail: onset time and

date, offset time and date, description of event, severity and relationship to IMP, action taken and outcome.

Adverse events ongoing from study GBT440-001 will be recorded and identified in the CRF as being ongoing from study GBT440-001 for Cohorts 15 or 17.

Adverse events will be recorded beginning with administration of study drug in GBT440-024.

All adverse events should be followed until recovery to the normal state has been achieved. In the event of a subject not returning to the clinical unit, the outcome of this event will be recorded as lost at follow up.

Diagnosis versus Signs and Symptoms

If known, a diagnosis should be recorded on the CRF rather than individual signs and symptoms (e.g. record only liver failure or hepatitis rather than jaundice, asterixis, and elevated transaminases). However, if a constellation of signs and/or symptoms cannot be medically characterized as a single diagnosis or syndrome at the time of reporting, each individual event should be recorded as an AE or SAE on the CRF. If a diagnosis is subsequently established, it should be reported as follow-up information.

Adverse Events Occurring Secondary to Other Events

In general, AEs occurring secondary to other events (e.g. cascade events or clinical sequelae) should be identified by their primary cause. For example, if severe diarrhea is known to have resulted in dehydration, it is sufficient to record only diarrhea as an AE or SAE on the CRF.

However, medically significant AEs occurring secondary to an initiating event that are separated in time should be recorded as independent events on the CRF. For example, if a severe gastrointestinal haemorrhage leads to renal failure, both events should be recorded separately on the CRF.

Persistent or Recurrent Adverse Events

A persistent AE is one that extends continuously, without resolution between patient evaluation time points. Such events should only be recorded once in the CRF unless their severity increases. If a persistent AE becomes more severe, it should be recorded again on the CRF.

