The following events are events of special interest and will need to be reported to the Sponsor’s medical representative [name], MPhil, MD, FACC within 24 hours, irrespective of regulatory seriousness criteria: any suspected drug

hypersensitivity reactions. Suspected drug hypersensitivity includes but is not limited to any occurrence of two or more of the following: fever, rash or lymphadenopathy.

Reporting of SAEs and SUSARs

SAEs occurring on this study will be reported to the Sponsor's medical representative [name], MPhil, MD, FACC within 24 hours. The Principal Investigator will be requested to complete a separate SAE reporting form in addition to the information on the CRF and in the AE book.

The Medicines for Human Use (Clinical Trials) Regulations 2004 (Statutory Instrument 1031) and subsequent amendments define the following terms:

A suspected unexpected serious adverse reaction (SUSAR) which is fatal or life-threatening must be reported to the competent authority and ethics committee immediately (within 7 days) after the Sponsor became aware of the event. Any additional information must be reported within 8 days of sending the first report.

A SUSAR which is not fatal or life-threatening must be reported to the competent authority and ethics committee as soon as possible (within 15 days) after the Sponsor becomes aware of the event.

If a clinical trial is being conducted at a trial site in a third country in addition to sites in the United Kingdom, the Sponsor of that trial shall ensure that all SUSARs occurring at that site are entered into the European database established in accordance with Article 11 of the EU Clinical Trials Directive.

As soon as practicable after the end of the reporting year, a Sponsor shall, in relation to each IMP tested in clinical trials in the United Kingdom for which he is the Sponsor provide the licensing authority and the relevant ethics committees with -

- A list of all the suspected serious adverse reactions which have occurred during that year in relation to:
 - those trials, whether at trial sites in the United Kingdom or elsewhere;
 - or any other trials relating to that product which are conducted outside the United Kingdom and for which he is the Sponsor;
- including those reactions relating to any investigational medicinal product used as a placebo or as a reference in those trials; and
- A report on the safety of the subjects of those trials.

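### Section 9.3.1 defines an SAE in terms of a drug-related reaction, so, read literally, serious events judged unrelated fall outside the 24-hour report and the SAE form

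*Combined protocol and SAP*

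**What the plan says.** Section 9.3.1 sets out its terms in sequence.

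- An adverse event is an untoward occurrence "which does not necessarily have to have a causal relationship with this treatment".
- An adverse drug reaction is "Any untoward and unintended response in a subject to an IMP which is related to any dose administered to that subject".
- Under the next heading, for serious adverse events, the list of criteria (death, threat to life, hospitalisation and so on) begins "An adverse reaction is ‘serious’ if it".

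Section 9.3.2 then builds on the term. Under its heading on SAEs and SUSARs, "SAEs occurring on this study will be reported" to the sponsor's medical representative within 24 hours, and the investigator completes a separate SAE form. The same section requires all AEs to be recorded "whether or not they are considered to be drug-related".

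Elsewhere the term is used more widely. Section 8.3 lists a "Grade ≥ 3 drug-related SAE" among the grounds on which study drug may be discontinued.

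**The concern.** Because section 9.3.1 has just separated event from reaction, the second word cannot be read as a loose synonym for the first. As worded, causality becomes part of the definition of an SAE, and the investigator's relatedness judgement decides whether a serious event enters the SAE process at all.

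Safety and tolerability are the primary objective (section 6.1). The study is open label with a single arm (section 7.1), so relatedness is judged with treatment known and without a concurrent control. A serious-event record that depends on that judgement is less informative than one that does not. The SUSAR clocks in section 9.3.2 also run from the sponsor's awareness. If an event first judged unrelated is not sent promptly, any later revision of that judgement starts from a late date.

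**Working it through.** No arithmetic applies. The check sets the definition beside every rule and statement that uses the term.

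**1. Is there another definition?** No. Section 9.3.1 is the only place where the criteria for an SAE are given.

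**2. Which rules depend on it?** The 24-hour report and the separate SAE form in section 9.3.2 are both triggered by an SAE. The only other 24-hour trigger in that section is suspected drug hypersensitivity, reportable whether or not it is serious. Nothing in the section extends the 24-hour rule to unrelated serious events in general.

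**3. How is the term used elsewhere?**

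| Section | Use of the term | Fits a reaction-only definition? |
|---|---|---|
| 5.3 | Reports that no drug-related SAEs have occurred | No: the qualifier would be redundant |
| 7.2.3.4 | Miscarriage and congenital abnormality are SAEs, with no causality condition | No |
| 8.3 | Drug-related SAE as one ground for discontinuation | No: redundant again |
| 9.3.2, recording rules | AE and SAE paired throughout, with no causality condition | No |
| 9.3.2, annual report | Suspected serious adverse reactions listed under their own name | Implies that SAE means something wider |

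Each of these points to an all-causality meaning. The line in section 9.3.1 is the exception, but it is also the definition.

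**4. What happens to an unrelated serious event under the literal text?**

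- It is still an AE, so it goes into the AE book and the CRF.
- Section 9.3.2 lists what to record for each AE: timing, description, severity, relationship, action and outcome. Seriousness is not on that list. The outcome categories in section 9.3.6 are resolved, ongoing and lost to follow-up, with no category for death. The AE record as described therefore need not show that an event was serious. The CRF itself is not in the documents and may carry such an item.
- If the event leads to a change in study drug, section 8.3 asks for the medical monitor to be told, typically within 48 hours. If it does not, the next scheduled look described is the Safety Monitoring Committee's review of cumulative data, at least monthly (section 7.1).

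**5. What do the planned summaries say?** Section 12.5 says only that adverse events are tabulated and summarised. Section 12.0 leaves detail to a separate analysis plan, whose text is not in what was supplied. No all-causality SAE table is specified that would make up for the definition.

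**6. What is not part of the defect?** Unexpectedness and SUSARs are defined on reactions, and that is consistent with their purpose in section 9.3.2.

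**The case against.** The strongest reply is that this is one misworded line. The heading says event, the working text treats SAEs as events of any cause, and site staff are likely to apply that meaning. This stands as to intent: the evidence favours a drafting slip over a deliberate exclusion. It does not remove the problem. The slip sits in the only definition, and section 15.2 tells sites to follow the protocol's instructions exactly.

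The second reply is that nothing is lost, since all AEs are recorded with their relationship and the committee reviews cumulative data. This stands too, and it confines the point to classification, speed of reporting and SAE counts.

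A reader might infer more in three directions, and the documents do not support any of them.

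- *That the individual stopping rule fails.* Section 7.1.1 names an SAE or a clinically significant non-serious AE, and turns on the opinion of the investigator or medical monitor. Section 8.3 separately allows discontinuation for any AE at the investigator's discretion. An unrelated serious event can lead to stopping whatever its label.
- *That sickle-related events are the ones mainly affected.* Section 9.3.2 has its own rule for them: complications are recorded as an AE or SAE only if judged to have worsened unexpectedly or changed in nature. That filter is not about drug causality, it acts earlier, and correcting the SAE definition leaves it untouched.
- *That SAE incidence is understated by a calculable amount.* The documents give no expected SAE rate, no expected share judged unrelated and no SAE incidence table. Any percentage would rest on invented inputs.

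**Conclusion.** The point holds as an internal contradiction in an operative safety definition. On the literal text, serious events judged unrelated are not SAEs. They escape the 24-hour sponsor report and the SAE form, and they may not be classed as serious in the summaries. Five other uses of the term assume the opposite.

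The size is qualitative. For an affected event that does not change study drug, the scheduled safeguard described moves from a 24-hour report to a review held at least monthly. No effect on an incidence figure can be stated.

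The conclusion rests on two conditions: that a site applies section 9.3.1 as written, and that the CRF and the separate analysis plan, neither of which was available, do not already impose an all-causality definition. If either condition fails, the practical effect is small, but the text still needs to agree with itself.

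**What to change.** - In section 9.3.1, define an SAE as any adverse event that meets at least one of the listed seriousness criteria, regardless of causality.
- Keep serious adverse reaction as a separate term, meaning an SAE judged related, for SUSAR and annual reporting.
- In section 12.5 or the separate analysis plan, state that SAEs are summarised regardless of causality, with drug-related SAEs as a subset. If that plan already says so, only the definition has to change.

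The cost is a short protocol wording change and possibly a few more 24-hour reports. No visit, sample or additional subject is needed.

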9.3.2 Reporting of Adverse Events

All AEs must be fully recorded in the AE book throughout the entire study period and will be transcribed into the subjects’ CRF, whether or not they are considered to be drug-related. Signs and symptoms of each AE should be described in detail: onset time and

date, offset time and date, description of event, severity and relationship to IMP, action taken and outcome.

Adverse events ongoing from study GBT440-001 will be recorded and identified in the CRF as being ongoing from study GBT440-001 for Cohorts 15 or 17.

Adverse events will be recorded beginning with administration of study drug in GBT440-024.

All adverse events should be followed until recovery to the normal state has been achieved. In the event of a subject not returning to the clinical unit, the outcome of this event will be recorded as lost at follow up.

Diagnosis versus Signs and Symptoms

If known, a diagnosis should be recorded on the CRF rather than individual signs and symptoms (e.g. record only liver failure or hepatitis rather than jaundice, asterixis, and elevated transaminases). However, if a constellation of signs and/or symptoms cannot be medically characterized as a single diagnosis or syndrome at the time of reporting, each individual event should be recorded as an AE or SAE on the CRF. If a diagnosis is subsequently established, it should be reported as follow-up information.

Adverse Events Occurring Secondary to Other Events

In general, AEs occurring secondary to other events (e.g. cascade events or clinical sequelae) should be identified by their primary cause. For example, if severe diarrhea is known to have resulted in dehydration, it is sufficient to record only diarrhea as an AE or SAE on the CRF.

However, medically significant AEs occurring secondary to an initiating event that are separated in time should be recorded as independent events on the CRF. For example, if a severe gastrointestinal haemorrhage leads to renal failure, both events should be recorded separately on the CRF.

Persistent or Recurrent Adverse Events

A persistent AE is one that extends continuously, without resolution between patient evaluation time points. Such events should only be recorded once in the CRF unless their severity increases. If a persistent AE becomes more severe, it should be recorded again on the CRF.

A recurrent AE is one that occurs and resolves between patient evaluation time points and subsequently recurs. All recurrent AEs should be recorded on the CRF.

Abnormal Laboratory Values

Only clinically significant laboratory abnormalities that require active management will be recorded as AEs or SAEs on the CRF (e.g. abnormalities that require study drug dose modification, discontinuation of study treatment, more frequent follow-up assessments, further diagnostic investigation, etc.).

If the clinically significant laboratory abnormality is a sign of a disease or syndrome (e.g. alkaline phosphatase and bilirubin 5× the ULN associated with cholecystitis), only the diagnosis (e.g. cholecystitis) needs to be recorded on the CRF.

If the clinically significant laboratory abnormality is not a sign of a disease or syndrome, the abnormality itself should be recorded as an AE or SAE on the CRF. If the laboratory abnormality can be characterised by a precise clinical term, the clinical term should be recorded as the AE or SAE. For example, an elevated serum potassium level of 7.0 mEq/L should be recorded as “hyperkalemia.”

Observations of the same clinically significant laboratory abnormality from visit to visit should not be repeatedly recorded as AEs or SAEs on the Adverse Event CRF, unless their severity, seriousness, or etiology changes.

Preexisting Medical Conditions

A preexisting medical condition is one that is present at the start of the study. Such conditions should be recorded on the CRF.

A preexisting medical condition should be recorded as an AE or SAE only if the frequency, severity, or character of the condition worsens during the study. When recording such events on the CRF, it is important to convey the concept that the preexisting condition has changed by including applicable descriptors (e.g. “more frequent headaches”).

Worsening of Sickle Cell Disease

Complications related to SCD should be recorded as an AE or SAE only if judged by the investigator to have unexpectedly worsened in severity and/or frequency or changed in nature any time during the study. When recording an unanticipated worsening of SCD on the CRF, it is important to convey the concept that the condition has changed by including applicable descriptors (e.g. “expansion of nonhealing leg ulcer”). Specific SCD- related AEs will be tabulated and reported (see assessment of safety section).

Protocol-Defined Events of Special Interest

The following events are events of special interest and will need to be reported to the Sponsor’s medical representative [name], MPhil, MD, FACC within 24 hours, irrespective of regulatory seriousness criteria: any suspected drug

hypersensitivity reactions. Suspected drug hypersensitivity includes but is not limited to any occurrence of two or more of the following: fever, rash or lymphadenopathy.

Reporting of SAEs and SUSARs

SAEs occurring on this study will be reported to the Sponsor's medical representative [name], MPhil, MD, FACC within 24 hours. The Principal Investigator will be requested to complete a separate SAE reporting form in addition to the information on the CRF and in the AE book.

The Medicines for Human Use (Clinical Trials) Regulations 2004 (Statutory Instrument 1031) and subsequent amendments define the following terms:

A suspected unexpected serious adverse reaction (SUSAR) which is fatal or life-threatening must be reported to the competent authority and ethics committee immediately (within 7 days) after the Sponsor became aware of the event. Any additional information must be reported within 8 days of sending the first report.

A SUSAR which is not fatal or life-threatening must be reported to the competent authority and ethics committee as soon as possible (within 15 days) after the Sponsor becomes aware of the event.

If a clinical trial is being conducted at a trial site in a third country in addition to sites in the United Kingdom, the Sponsor of that trial shall ensure that all SUSARs occurring at that site are entered into the European database established in accordance with Article 11 of the EU Clinical Trials Directive.

As soon as practicable after the end of the reporting year, a Sponsor shall, in relation to each IMP tested in clinical trials in the United Kingdom for which he is the Sponsor provide the licensing authority and the relevant ethics committees with -

- A list of all the suspected serious adverse reactions which have occurred during that year in relation to:
 - those trials, whether at trial sites in the United Kingdom or elsewhere;
 - or any other trials relating to that product which are conducted outside the United Kingdom and for which he is the Sponsor;
- including those reactions relating to any investigational medicinal product used as a placebo or as a reference in those trials; and
- A report on the safety of the subjects of those trials.

